4.4.2.3.1 Statistical Hypothesis, Model and Method of Analysis

The analysis is same as the key secondary endpoint and the details will be obtained from the MMRM detailed in [Section 4.4.2.1.1](#). Also, the results will be presented in Table 14.2.3.2.1.

4.4.2.3.2 Supportive Analyses

A PP analysis will be performed on the change from baseline in tactile threshold (g) as detailed in [Section 4.4.2.1.2](#). The results will be presented in Table 14.2.3.1.2 and Table 14.2.3.2.2

Haleon Confidential

CCI

Statistical Analysis Plan Template v6.0

Page 21 of 40

respectively for summary table and analysis table. Also, Figure 14.2.2.2.2 will be generated for all subjects in PP population.

4.4.2.4 Change from Baseline in DHEQ-48 endpoints at Day 56 and Day 28

DHEQ-48:

The DHEQ-48 is a condition-specific measure of OHrQoL in relation to DH (Boiko, 2010) that has been previously validated in longitudinal studies and shown to be responsive to treatment (Baker, 2014). The DHEQ total score can be broken down into 5 separate ‘domain’ scores to provide a more granular understanding of the specific areas of improvement subjects experience in their OHrQoL.

- **Restrictions:** Derived from participant responses to Section 2, Q1-4 (‘the ways in which any sensations in your teeth affect you in your daily life’).
- **Adaptation:** Derived from participant responses to Section 2, Q5-16 (‘the ways in which the sensations in your teeth have forced you to change things in your daily life’; ‘things you do in your daily life to avoid experiencing the sensations in your teeth’).
- **Social Impact:** Derived from participant responses to Section 2, Q17-21 (‘the way the sensations affect you when you are with other people or in certain situations’).
- **Emotional Impact:** Derived from participant responses to Section 2, Q22-29 (‘the way the sensations in your teeth make you feel’).
- **Identity:** Derived from participant responses to Section 2, Q30-34 (‘what the sensations in your teeth mean for you’).

The DHEQ also provides specific information on how much the sensations in the participant’s teeth affect their life overall:

- **Global Oral Health:** Derived from participant response to Section 2, Q35 (‘rate the health of your mouth, teeth and gums’).
- **Effect on Life Overall:** Derived from participant responses to Section 2, Q36-39 (impact of DH on overall quality of life).

The other secondary efficacy endpoints will be the change from baseline in DHEQ-48 endpoints (as described below) at respective visits for each study product.

Change from Baseline will be calculated at Day 28 and Day 56 for all DHEQ endpoints.

Section 1

1. Impact on Everyday Life: Q7, Q8 & Q9 (separate scores)

Section 2

1. DHEQ Total Score (sum of Q1-34)
2. DHEQ Restrictions Domain score (sum of Q1-4)

-
3. DHEQ Adaptation Domain score (sum of Q5-16)
 4. DHEQ Social Impact Domain score (sum of Q17-21)
 5. DHEQ Emotional Impact Domain score (sum of Q22-29)
 6. DHEQ Identity Domain score (sum of Q30-34)
 7. DHEQ Global Oral Health Score (Q35)
 8. DHEQ Effect on Life Overall Score (sum of Q36-Q39)

Change from Baseline will be calculated at the subject-level first then mean change from Baseline will be calculated for each DHEQ endpoint (mentioned above) across all subjects.

Descriptive statistics (n, mean, SD, standard error [SE], median, minimum, and maximum) will be presented for each DHEQ-48 endpoint (mentioned above) at each assessment time point in Table 14.2.4.1.1 and 14.2.5.1-8.1.1, for Section 1 and Section 2 respectively and for all subjects in mITT population by study product. Raw means (\pm SE) for each DHEQ endpoint, and the individual DHEQ questions, at each assessment will be plotted by study product in Figure 14.2.3.1 and Figure 14.2.2.3-10.1, for Section 1 and Section 2 respectively and for all subjects in mITT population.

Individual DHEQ endpoint data for each endpoint (mentioned above) will be listed for each subject by visit and study product group in Listing 16.2.6.5, 16.2.6.6.1-7, for Section 1 and Section 2 respectively, for all randomized subjects.

4.4.2.4.1 Statistical Hypothesis, Model and Method of Analysis

The following null and alternative hypotheses will be evaluated:

- H_0 : There is no difference between baseline and post-baseline (Day 28, Day 56)
- H_1 : There is a difference between baseline and post-baseline (Day 28, Day 56)

Change from Baseline for each DHEQ endpoint listed above will be analyzed using a MMRM with visit and stratification [maximum Baseline Schiff sensitivity score of the two 'Test Teeth' (2 or 3)] as fixed effects, and the respective Baseline DHEQ score as a covariate. Subject will be included as a repeated measure with unstructured covariance matrix. Kenward-Roger's degrees of freedom will be applied. The estimates of the adjusted mean (SE) change from Baseline will be presented along with 95% CIs for each treatment group. In the event that the model does not converge on the unstructured covariance matrix, an appropriate alternative will be considered.

Using the above model, the adjusted mean change from baseline in each DHEQ endpoint listed above will be reported by study product group along with 95% CIs and p-values testing for a non-zero change from baseline will be provided in Table 14.2.4.2.1 and 14.2.5.1-8.2.1, for Section 1 and Section 2 respectively.

The assumptions of normality and homogeneity of variance in the MMRM will be investigated. In case of violation of these assumptions, a suitable non-parametric test (Wilcoxon Signed Rank Test) will be performed to assess the change from Baseline comparison (Post-Baseline vs. Baseline); the results will be provided to support the MMRM results.

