1 PROTOCOL SUMMARY

1.1 Synopsis

Summary Title:

Clinical study to evaluate the anti-sensitivity efficacy of a calcium sodium phosphosilicate toothpaste in a population of dentin hypersensitivity sufferers.

Background and Rationale for the Study:

Calcium sodium phosphosilicate (CSPS) is a particulate, bioactive material incorporated into oral healthcare products for the relief of dentin hypersensitivity (DH). CSPS acts to relieve DH by the physical occlusion of exposed dentin tubules and was first marketed in a fluoridated, daily use anti-sensitivity toothpaste by GlaxoSmithKline (now Haleon) in 2011.

Randomized controlled clinical trials (with 4-12 weeks treatment duration) support the longer-term anti-sensitivity efficacy of 5% w/w CSPS-containing toothpastes with twice daily use. The aim of the current 8-week study is to confirm the clinical DH efficacy of a 5% CSPS toothpaste. Changes to the formulation, compared to those previously investigated by the sponsor, include removal of the opacifier, addition of a blue pigment, introduction of a new flavor for improved in-use experience, and modification of the dental abrasive system for improved stain removal and enamel polishing benefits. None these changes are expected to impact the occlusion mode of action (MoA) of CSPS and the anti-sensitivity efficacy of a 5% CSPS toothpaste.

In addition to confirming the longer-term DH efficacy of the investigational 5% CSPS toothpaste, time to onset of DH relief will be investigated, with clinical assessments completed after 3-, 7-, 14- and 28-days twice-daily use. At each post-Baseline time point, the efficacy of the 5% CSPS toothpaste will be compared with that of a regular fluoride toothpaste with no known anti-sensitivity efficacy (negative control).

Objectives and Endpoints:

| Objectives | Endpoints |
|---|--|
| Efficacy | |
| Primary | |
| To demonstrate the clinical efficacy of a 5% CSPS toothpaste in reducing DH to an evaporative (air) stimulus (as measured by Schiff sensitivity score), compared to a negative control toothpaste, after 8 weeks twice daily use. | Change from Baseline in Schiff sensitivity score at Day 56 (Week 8). |
| Secondary | |
| To demonstrate the clinical efficacy of a 5% CSPS toothpaste in reducing DH to a tactile stimulus (as measured by tactile threshold in grams [g]), compared to a negative control toothpaste, after 8 weeks twice daily use. | Change from Baseline in tactile threshold (g) at Day 56 (Week 8). |

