Clinical trials evaluating pain-related endpoints can be prone to ‘placebo effects’ ([Addy, 1985](#); [West, 1997](#)); such effects are frequently observed in DH studies. A study conducted to evaluate the natural history of the DH condition also highlighted the existence of a ‘no treatment’ effect, characterized by an improvement in sensitivity simply as a result of study participation ([Leight, 2008](#)). To help minimize the potential impact of such effects, an acclimatization period (14-28 days duration) will precede the Baseline visit. During this period, study subjects will brush twice daily with the regular fluoride toothpaste and toothbrush provided (in place of their own oral hygiene products) and record each brushing occasion in a diary. The acclimatization period will also serve to standardize oral hygiene practice across the study population and familiarize participants with several important study procedures (e.g., toothpaste dosage, timed brushings, diary completion) prior to treatment.

DH is an episodic condition; symptoms are known to vary spontaneously ([West, 2008](#), [West, 2013](#)). Baseline clinical values that would support enrolment may represent random highs that could be followed by regression to the mean, leaving the subject or selected test tooth without the condition under investigation (i.e., DH) during the treatment period. To help minimize the potential for this to occur in the current study, randomized subjects will be required to demonstrate consistency in response to both DH stimuli at both the Screening and Baseline visits. Qualifying subjects will have a minimum of two eligible teeth with a tactile threshold \leq 20g and a Schiff sensitivity score ≥ 2 at both Screening and Baseline. In line with published guidelines for the design and conduct of studies investigating the clinical efficacy of anti-sensitivity products, inconsistent responders will be excluded ([Holland, 1997](#)).

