The assumptions of normality and homogeneity of variance in each MMRM will be investigated. In case of violation of these assumptions, a suitable non-parametric test (adjusted for the randomization stratification value) will be performed to assess change from Baseline comparisons (Test Toothpaste vs. Reference Toothpaste at Days 56, 28, 14, 7 and 3, as appropriate); the results will be provided to support the MMRM results.

DHEQ-48

Change from Baseline will be calculated at Day 28 and Day 56 for all DHEQ endpoints.

- **Section 1**
 - Impact on Everyday Life: Q7, Q8 & Q9 (separate scores)
- **Section 2**
 - DHEQ Total Score (sum of Q1-34)
 - DHEQ Restrictions Domain score (sum of Q1-4)
 - DHEQ Adaptation Domain score (sum of Q5-16)
 - DHEQ Social Impact Domain score (sum of Q17-21)
 - DHEQ Emotional Impact Domain score (sum of Q22-29)
 - DHEQ Identity Domain score (sum of Q30-34)
 - DHEQ Global Oral Health (Q35)
 - DHEQ Effect on Life Overall (sum of Q36-Q39)

Change from Baseline will be calculated at the subject-level first then mean change from Baseline will be calculated for each DHEQ endpoint across all subjects.

Change from Baseline for each DHEQ endpoint listed above will be analyzed using a MMRM with time point and maximum Baseline Schiff sensitivity score of the two 'Test Teeth' (2 or 3) as fixed effects, and the respective Baseline DHEQ score as a covariate. Subject will be included

Property of Haleon- Confidential

May not be used, divulged, published or otherwise disclosed without the consent of Haleon

as a repeated measure with unstructured covariance matrix. Kenward-Rogers degrees of freedom will be applied. The estimates of the adjusted mean (SE) change from Baseline will be presented along with 95% Cis for each treatment group.

For each DHEQ endpoint listed above, and each individual DHEQ question, the value at each timepoint (Baseline, Day 28 and Day 56) and the corresponding change from Baseline will be summarized descriptively for each treatment group. Raw means (\pm SE) for each DHEQ endpoint, and the individual DHEQ questions, at each assessment timepoint will be plotted by treatment group.

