| 8) I have to cool some foods or drinks down before I can have them. |  |  |  |  |  |  |  |
| 9) I have to cut up some fruits before being able to eat them. |  |  |  |  |  |  |  |
| 10) I have to wear a scarf over my mouth on cold days. |  |  |  |  |  |  |  |

The following questions are **about the things you do in your daily life to avoid experiencing the sensations in your teeth**. Thinking about yourself ***over the last month*** to what extent would you agree or disagree with the following statements (Please tick only one response for each question).

| | Strongly agree (7) | Agree (6) | Agree a little (5) | Neither agree nor disagree (4) | Disagree a little (3) | Disagree (2) | Strongly disagree (1) |
|---|--------------------------|--------------------------|--------------------------|--------------------------------|--------------------------|--------------------------|--------------------------|
| 11) I have avoided very cold drinks or foods. |  |  |  |  |  |  |  |
| 12) I have avoided very hot drinks or foods. |  |  |  |  |  |  |  |
| 13) When eating some foods I have made sure they don't touch certain teeth. |  |  |  |  |  |  |  |
| 14) I have changed the way I brush my teeth. |  |  |  |  |  |  |  |

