1.4 Sample Size Calculation

Sufficient subjects will be screened and entered into the acclimatization period to randomize approximately 234 subjects to study product (approximately 117 subjects per treatment group) to ensure approximately 210 complete the study (approximately 105 subjects per treatment group), allowing for approximately 10% dropouts.

The study will be sufficiently powered to demonstrate statistical superiority of the Test Toothpaste compared to the Reference Toothpaste (negative control) for the change from Baseline in the Schiff sensitivity score after 56 days, i.e., 8 weeks, (primary objective) and 3 days (key secondary objective, earliest time point) treatment. It is anticipated that the treatment effect will increase over time. A sample size of 105 evaluable subjects per treatment group will provide 90% power to detect a mean difference of 0.25 units (SD = 0.55) in change from Baseline in Schiff sensitivity score after 3 days treatment, using a 2-tailed 2-sample t-test with a 5% significance level. The sample size calculation was performed using PASS software version 23.0.1.

The dropout rate and SD estimates are based on the results of DH efficacy studies of similar design and duration (Clinical Studies CCI [REDACTED] and CCI [REDACTED] sponsor data held on file, available on request).

2 Planned Analyses

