4.4 Analysis of Efficacy

The primary population for assessment of efficacy will be the mITT Population.

All p-values presented will be two-sided and assessed at the 5% significance level. A sequential testing strategy will be used to adjust for multiplicity for the comparisons between the Test and Reference Toothpastes in change from Baseline in Schiff sensitivity score and tactile threshold (g) at each assessment time point.

At each timepoint, change from Baseline in tactile threshold (g) will only be assessed for confirmatory evidence if the change from Baseline in Schiff sensitivity score achieves a statistically significant greater reduction for the Test Toothpaste compared to Reference Toothpaste (negative control). This strategy will begin at Day 56, then move to successively earlier timepoints (i.e., Day 56 → Day 28 → Day 14 → Day 7 → Day 3), only moving the next earlier timepoint for confirmatory evidence if all later timepoints achieve statistically significant greater reductions for the Test Toothpaste compared to Reference Toothpaste (negative control) for both Schiff sensitivity score and tactile threshold (g). There will be no further adjustments for multiplicity for the other secondary endpoints (DHEQ-48).

The results from each MMRM will be tabulated, presenting the following information, in addition to the results specified for the primary and secondary analyses below: least square mean change from Baseline for each study product at Days 3, 7, 14, 28 and 56 (based on the observed stratification margins for those MMRM with a term for randomized strata) and used to test for any change from Baseline, with two-sided p-values and 95% CIs.

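### DHEQ-48 is formally tested only against Baseline and no Test-minus-Reference estimate is planned, so its p-values cannot be attributed to the toothpaste

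*SAP*

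**What the plan says.** **Status of the endpoint.** DHEQ-48 is listed among the secondary efficacy endpoints (Protocol 3; SAP 1.2). Its objective is to describe what subjects perceive with their assigned toothpaste. Unlike the Schiff and tactile objectives, it does not mention the negative control. Protocol 12.3 and SAP 4.4 leave DHEQ out of the sequential strategy, and study success depends only on Schiff score at Day 56.

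**Hypothesis and tests.** SAP 4.4.2.4.1 gives the null as "There is no difference between baseline and post-baseline (Day 28, Day 56". It calls for p-values for non-zero change and, if model assumptions fail, a Wilcoxon signed-rank test of post-Baseline against Baseline. SAP 4.4 adds: "All p-values presented will be two-sided and assessed at the 5% significance level". The hypothesis pair and the signed-rank test appear in the SAP but not in Protocol 12.3.2, although SAP section 5 declares no change from the protocol.

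**Model.** Both documents list visit (or time point), the Schiff stratum and the Baseline DHEQ score. Neither lists study product. Both still promise results by arm; the protocol's adjusted mean changes "will be presented along with 95% Cis for each treatment group". By contrast, the Schiff and tactile hypotheses (SAP 4.4.1.2 and 4.4.2.1.1) are Test versus Reference, from models with product and product-by-visit terms.

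**Background effects.** Protocol 4.2 says placebo effects are frequent in this field and describes a no-treatment effect "characterized by an improvement in sensitivity simply as a result of study participation". It also says that symptoms vary spontaneously and that high Baseline clinical values may regress. It offers the acclimatization period and double qualification as ways to reduce these effects, not to remove them.

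**The concern.** A before-after test answers whether DHEQ changed, not whether the toothpaste changed it. The effects named in Protocol 4.2 can lower DHEQ scores in either arm, and the concurrent negative control is the design's means of removing whatever is common to both. The planned DHEQ tests do not use it.

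At stake is the reading of the quality-of-life result. A report could show significant improvement on Test, on Reference or on both without any product effect. It would contain no estimate of the difference that a randomized, controlled design can provide.

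**Working it through.** **Inputs.** Two-sided 5% level (SAP 4.4) and 105 evaluable subjects per group (SAP 1.4). No DHEQ effect size or SD is given, so drift is expressed in SDs of the change score and is an assumption.

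**1. The plan's own figure.** SAP 1.4 states: "A sample size of 105 evaluable subjects per treatment group will provide 90% power" for "a mean difference of 0.25 units (SD = 0.55) in change from Baseline in Schiff sensitivity score after 3 days treatment". Normal approximation: n = 2 × (1.960 + 1.282)² × (0.55 / 0.25)² = 2 × 10.51 × 4.84 = 101.7, so 102 per arm. The exact t-test needs 103, and power at 105 is 90.6%. For dropout, 105 / 0.90 = 116.7, so 117 per arm and 234 in total. The stated size reproduces and is not in dispute, but it concerns Schiff score, not DHEQ.

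**2. Within-arm test with zero product effect.** Let both arms drift by s SD. The one-sample t statistic has 104 degrees of freedom, critical value 1.983 and noncentrality s × √105 = 10.25 s. Let p be the chance that a given arm is significant. The chance that exactly one of two independent arms is significant is 2p(1 − p).

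| Common drift s (SD) | Noncentrality | Given arm significant | Exactly one arm significant | Between-product test |
|---|---|---|---|---|
| 0 | 0 | 5% | 9.5% | 5% |
| 0.1 | 1.02 | 17% | 28.7% | 5% |
| 0.2 | 2.05 | 53% | 49.8% | 5% |
| 0.3 | 3.07 | 86% | 23.9% | 5% |
| 0.4 | 4.10 | 98% | 3.5% | 5% |
| 0.5 | 5.12 | 99.9% | 0.2% | 5% |

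The last column is constant because the drift cancels: the noncentrality is (s − s) / √(2/105) = 0. A simulation with Baseline adjustment (5,000 runs at each of 0, 0.2, 0.3 and 0.5 SD, assumed slope −0.4) rejected in 4.7% to 5.2% of runs for the between-product contrast. Its within-arm rates at 0.2, 0.3 and 0.5 SD were 59%, 90% and more than 99%; they are higher because adjustment reduces the residual SD.

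**3. Number of tests.** Section 1 Q7, Q8 and Q9 plus eight Section 2 scores make 11 endpoints. Over 2 visits and 2 products that is 11 × 2 × 2 = 44 p-values, if the model is fitted by product. Taken literally, the listed model pools the arms (n = 210). It then yields 11 × 2 = 22 p-values and cannot give separate adjusted means by product. Pooling raises the chance of significance to 82% at 0.2 SD and 99% at 0.3 SD.

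**4. What a between-product contrast could show.** The detectable difference is (1.960 + 0.842) × √(2/105) = 0.39 SD at 80% power, and (1.960 + 1.282) × √(2/105) = 0.45 SD at 90%.

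**5. Recall window, Section 2 Q1-34 only.** These items ask about the past month, while the run-in lasts 14 to 28 days. Taking a month as 30 days, (30 − 14)/30 = 53% of the Baseline window precedes Screening with the shortest run-in, and (30 − 28)/30 = 7% with the longest. For these items the run-in cannot fully take the participation effect out of the Baseline score. Section 1 Q7-9 carry no such wording, and Q35-39 could not be checked.

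**The case against.** **The analysis fits its objective.** The objective is to describe change within the assigned product, success does not depend on it, and no confirmatory claim is attached. This stands, and it limits the weight of the point. It does not rescue the tests: a descriptive objective needs no null hypothesis, p-value or signed-rank test.

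**The arms can be compared anyway.** By-product means, confidence intervals and plots are planned. A reader might infer that the DHEQ output as a whole says nothing about the product; that goes too far, because randomized arms shown side by side allow an informal comparison. Comparing significance between arms is still unsafe: at 0.2 SD drift exactly one arm is significant about half the time with no product effect.

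**Stronger readings the documents do not support.**
- A reader might infer that the plan breaks a promise in the Synopsis: "At each post-Baseline time point, the efficacy of the 5% CSPS toothpaste will be compared with that of a regular fluoride toothpaste". That sentence follows the list of clinical assessments, including Days 3, 7 and 14, when DHEQ is not collected. It concerns clinical efficacy.
- A reader might infer a seasonal effect from items such as "I have to wear a scarf over my mouth on cold days". No section describes one.
- A reader might infer that subjects are selected at a DHEQ high. Entry is on tactile threshold and Schiff score, at two visits; DHEQ is not an entry criterion, so any regression in it is indirect.

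**Cancellation may be incomplete.** Only Test subjects are shown their Test Teeth and told to brush them first (Protocol 6.2 and 8.2.1.9). This stands: the contrast would estimate product together with its usage instruction.

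**Conclusion.** The point holds for the planned tests and for the missing between-product estimate, and no further. A significant before-after DHEQ p-value would not by itself be evidence of a toothpaste effect. Under an assumed common drift of 0.2 to 0.5 SD and no product effect, such a result is expected in a given arm about 53% to more than 99% of the time. That range rests on the assumed drift, independent arms and 105 evaluable subjects per arm; the documents provide no DHEQ variability to narrow it.

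The primary result, the sample size and the confirmatory sequence are unaffected. This is a worthwhile and inexpensive correction to a secondary endpoint, not a threat to the trial's main conclusion.

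**What to change.** In SAP 4.4.2.4.1 and Protocol 12.3.2, before unblinding:

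- Add study product and study product × visit to the DHEQ model. Without them neither the promised by-product means nor a contrast can be computed from it.
- Report the least squares mean difference (Test minus Reference) with 95% CI at Days 28 and 56, labelled descriptive and outside the multiplicity sequence.
- Keep the by-product mean changes with their CIs.
- Drop the hypothesis pair, the p-values and the signed-rank tests against Baseline. Exempt DHEQ from the general paragraph in SAP 4.4 and Protocol 12.3 that calls for a test of change from Baseline from each MMRM.
- If a non-parametric back-up is kept, use the Van Elteren test already named in SAP 4.4.1.2, also labelled descriptive.

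Dropping the tests alone would remove the misleading p-values but leave no DHEQ estimate that uses the control arm. The full change costs document wording, two model terms and one contrast per visit in each DHEQ table. The downside is that the DHEQ result may look less favourable than a before-after p-value.
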